8.2 SAFETY ASSESSMENTS

The primary safety assessment will be monitoring of blood glucose and frequency of hypoglycemia. All participants in the HIWL only and the control group will receive a blue tooth-connected digital glucometer. The participants will be instructed to monitor blood glucose at least twice daily, including once fasting and once 4-hours postprandial. Participants will also be instructed to monitor blood glucose if they feel symptoms of hypoglycemia. The study physicians will adjust medications as noted previously based on self-monitored blood glucose and reported episodes of hypoglycemia. For individuals in the HIWL + CGM arms, the monitoring of blood glucose will be continuous.

Participants in the active intervention arm will also have safety monitoring as part of their treatment protocol while initiating weight loss with the HIWL dietary strategy. [name] will be responsible for reviewing the chemistry panels that will be obtained at weeks 2, 4, 6, 8, 12, and 16. He will adjust the treatment plan including making adjustments in the dietary prescription or concomitant medications to resolve any abnormalities.

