2.3 RISK/BENEFIT ASSESSMENT

2.3.1 KNOWN POTENTIAL RISKS

There is some minor discomfort and risk of mild bruising during venipuncture.

A breach of participant confidentiality is an additional risk for each participant.

The participants in this study may also be subject to fluctuations in their blood glucose levels as a result of restricting calories and modifying the types of foods they are consuming. This could lead to symptomatic hypoglycemia.

Discomfort associated with venipuncture is rapidly reversible. Bruises from venipuncture will heal in several days. Hypoglycemia is reversible with appropriate therapy.

The continuous glucose monitor will be worn throughout the study for those in the High Intensity Weight Loss Group plus Continuous Glucose Monitoring group and by everyone else during study visits at baseline and weeks 12, 24, and end of study. Use of the continuous glucose monitor could be associated with some skin irritation from the adhesive or the filament that is under the skin. Some people will notice some discomfort with use of the monitor.

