Glycemic control: Serum HbA1c measurements will be drawn quarterly on all participants. Assessment of glycemic control will be done in the context of anti-diabetes medication usage. Documentation of medications will be obtained electronically from all available sources (e.g., EHR, pharmacy) and by physical review of medicines using the “brown bag” method. Participants will be requested to bring all of their medication to the clinic for review. Research assistants will reconcile medication regimens from the electronic record and those presented by the patient. Medicines will be described as any prescription or non-prescription substance they take on a regular basis including tablets, liquids, inhalers, creams and ointments. Continuous glucose monitoring (CGM) with sub-dermal sensors will be used as a secondary measure of glycemic control for all participants. CGM provides information beyond what traditional finger stick blood glucose testing affords. CGM provides measurements of interstitial blood glucose (BG) at 1- 15 minute intervals and correlates well with capillary blood glucose measurements. Collection of continuous glucose values allows immediate recognition of current BG and prediction of trajectory of BG; preventing hypoglycemia. We will utilize the FreeStyle Libre, which is one of the most frequently used CGM in the world as a result of both its accuracy and simplicity of use. Sensors are placed on the upper arm using a painless spring loaded injector. BG recordings are available within an hour and the device will record BG every 15 minute minutes without a need for calibrations for 2 weeks. CGM related outcomes that we will assess at baseline and 12 months include time in range, episodes of hypoglycemia, glucose variability, and average glucose. For individuals in the HIWL + CGM arm of the trial, data from the CGM they are using in the intervention will be used for these outcomes.

Diabetes remission: Diabetes remission status will be assessed at 12 months as a secondary outcome for this study. At the time of assessment, if the participant has achieved an HbA1c of 5.7-6.4% without the use of anti-diabetes medications, the participant will be classified as being in partial remission. If the participant has achieved an HbA1c of <5.7% without any medications, the participant will be classified as being in complete remission. The sum of these two outcomes will comprise the outcome of any remission (partial + complete).

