8.3 ADVERSE EVENTS AND SERIOUS ADVERSE EVENTS

Participants will be queried for side effects and specific adverse events (AE) at each in-person study visit using a standardized questionnaire. Blinded staff will enter data directly into our centralized study database. Should an AE be detected using this process, or by spontaneous report between visits, or if an AE is detected using physical or laboratory examination, a determination of relatedness to study intervention will be made by the study physician. Serious adverse events (SAE) will be reviewed by the study physician and reported to the IRB per local policy. We will examine the **total number of AEs and SAEs at 12 months** by study group, as well as several subcategories of events.

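### Hypoglycemia and adverse events are detected by different means in different arms, and the plan does not tie the between-arm safety comparison to a common source

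*Combined protocol and SAP*

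**What the plan says.** Section 8.2 opens its safety plan with: "The primary safety assessment will be monitoring of blood glucose and frequency of hypoglycemia". It then sets two measurement systems by randomized arm. For two arms: "All participants in the HIWL only and the control group will receive a blue tooth-connected digital glucometer", and "The participants will be instructed to monitor blood glucose at least twice daily, including once fasting and once 4-hours postprandial", with further tests when symptoms are felt. For the third: "For individuals in the HIWL + CGM arms, the monitoring of blood glucose will be continuous". Section 6.5.1 defines hypoglycemia as glucose below 70 mg/dL and has episodes ascertained at clinic visits.

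Some elements are common to all arms. Section 2.3.1 has the sensor worn all year in HIWL + CGM and "by everyone else during study visits at baseline and weeks 12, 24, and end of study", and the Schedule of Activities (Section 1.3) marks the same times. Section 8.1 lists sensor-detected hypoglycemia among the CGM outcomes for all participants, but only at baseline and 12 months. For HIWL + CGM, "data from the CGM they are using in the intervention will be used for these outcomes"; no length of window is given.

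On AEs, Section 8.3 says: "Participants will be queried for side effects and specific adverse events (AE) at each in-person study visit using a standardized questionnaire". It also admits events reported spontaneously or found by physical or laboratory examination, and then examines 12-month AE and SAE totals by study group. Section 8.2 describes chemistry panels at weeks 2, 4, 6, 8, 12 and 16 for the active intervention. Section 6.1.1 gives HIWL participants weekly clinician visits for four weeks and platform symptom surveys. DSME participants have one class or appointment in month 1 and at least quarterly appointments afterwards.

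**The concern.** Where the chance of seeing an event depends on the assigned arm, a raw comparison mixes true incidence with ascertainment. The more closely watched arm can look less safe when nothing differs.

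Two contrasts are exposed. For hypoglycemia it is HIWL + CGM against each of the other arms. The contrast with HIWL alone is the sharpest, because the sensor is the only planned difference between those two interventions. For AEs it is both HIWL arms against DSME, because extra contacts and laboratory panels feed the totals.

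Section 9 contains no safety analysis, so nothing there says which hypoglycemia source is compared or how unequal detection is handled.

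**Working it through.** The plan gives no safety figure to reproduce. Its only power statement concerns weight: a 12-point difference (15% minus 3%) with SD 6.8% and 30 per arm. With two-sided alpha 0.05 assumed, power exceeds 0.9999 at 30, 27 and 24 per arm, consistent with the stated figure of over 95%. It has no bearing on this point.

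**Readings per day.** Section 8.1 gives one sensor reading every 15 minutes, so 24 × 60 / 15 = 96 per day. Section 8.2 gives a glucometer minimum of 2. The ratio is 96 / 2 = 48 for HIWL + CGM against either other arm, and 1 for HIWL against DSME. This counts readings, not episodes detected.

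**Episodes detected (illustration).** Two inputs are assumptions, because the documents give neither:
- s, the share of episodes that prompt a test: 0.2, 0.5 or 0.8.
- D, episode length in minutes: 15 to 120.

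The sensor is taken to detect every episode. That follows from 15-minute readings if episodes last at least 15 minutes and the sensor is always worn and accurate. The two scheduled glucometer tests are treated as falling at random times relative to episodes. Then

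glucometer detection p = s + (1 − s) × 2D / 1440,

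and, with equal true rates, the apparent sensor-to-glucometer ratio is 1 / p. For D = 30 and s = 0.5: p = 0.5 + 0.5 × 60 / 1440 = 0.521, ratio 1.92. Cells show p, then the ratio:

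| D (min) | s = 0.2 | s = 0.5 | s = 0.8 |
|---|---|---|---|
| 15 | 0.217 (4.62) | 0.510 (1.96) | 0.804 (1.24) |
| 30 | 0.233 (4.29) | 0.521 (1.92) | 0.808 (1.24) |
| 60 | 0.267 (3.75) | 0.542 (1.85) | 0.817 (1.22) |
| 120 | 0.333 (3.00) | 0.583 (1.71) | 0.833 (1.20) |

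**Consequence for a test (illustration).** This simulation used 27 per arm (30 less 10% loss), 30-minute episodes, equal true rates of 2 to 12 episodes per person-year, gamma between-person variation with shape 1, and a t-test on square-root-transformed counts. A nominal 5% test rejected in about 93–99% of trials at s = 0.2, 41–56% at s = 0.5 and 9–10% at s = 0.8. With equal detection it rejected in about 5%.

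**AEs.** No ratio can be computed, but the routes can be set side by side:
- Questionnaire: the AE row of the Schedule is not split by arm and marks SV2 and weeks 12, 24 and 52. This route appears equal.
- Clinician contact in month 1: weekly visits in the HIWL arms, one class or appointment in DSME.
- Platform surveys: part of the HIWL intervention only.
- Chemistry panels: six, described in Section 8.2 for the active intervention. The corresponding Schedule row carries no arm label.

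Section 8.3 counts events from all these routes in one total, so that total is unequally ascertained even if the questionnaire is balanced.

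**The case against.** The strongest reply is that the plan poses no formal between-arm hypoglycemia question. Section 8.2 concerns monitoring and medication adjustment, Section 9.1 lists no hypoglycemia hypothesis, and nowhere does the plan say that year-round sensor counts will be set against finger-sticks. The one hypoglycemia outcome specified for everyone, in Section 8.1, already uses the sensor in all arms. This stands. A reader might infer that the trial cannot answer a primary safety question, but the documents do not pose one in that form. What remains is that Section 8.2's frequency has no named source and that Section 8.1 leaves the window length open and omits weeks 12 and 24.

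A reader might also infer that safety differences will mostly be detection, or will be 48-fold. Neither is supported:
- The 48 counts readings, uses the minimum testing frequency and ignores symptom-prompted tests.
- At the low end of the illustration the artefact is 1.2-fold.
- Real differences are plausible. Table 4 links the start of the weight-loss intervention to medication reduction, and Section 8.1 credits the sensor with helping to prevent hypoglycemia, which would pull the HIWL + CGM count down.

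Nor do the documents support a glucose-reading imbalance between HIWL and DSME. They share a device and an instruction, and Section 6.5.1 has DSME logs reviewed weekly.

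Finally, a reader might infer that the AE questionnaire is given at every HIWL treatment visit. Section 8.3 refers to study visits, and the Schedule points to common ones. The wording is at most ambiguous. The AE concern rests instead on the other routes, and the blinded data entry in Section 8.3 does not equalize those.

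**Conclusion.** The concern holds in limited form. Detection differs by randomized arm for hypoglycemia (HIWL + CGM against the other two) and for AEs (HIWL arms against DSME), and the plan does not account for it. Raw differences may substantially reflect detection.

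For hypoglycemia the illustrative artefact is about 1.2- to 4.6-fold with equal true rates. It depends on the assumed prompting share and episode length and on complete sensor detection. For AEs the size cannot be determined. SAEs are likely to be less sensitive to surveillance than minor or laboratory-detected events.

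This is a worthwhile clarification to make before data are compared by arm. It does not touch the weight endpoint.

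**What to change.** - **Hypoglycemia.** State that any between-arm comparison uses sensor episodes below 70 mg/dL per day of wear in the windows scheduled for everyone: baseline and weeks 12, 24 and 52. Take the same window length from all three arms. Section 8.1 gives a two-week sensor life but no required wear time, so the length must be written down. Use a rate model with a wear-time offset. The baseline window precedes randomization and can serve as a covariate. Report glucometer and continuous intervention data by arm descriptively only.
- **AEs.** Base the between-arm comparison on events elicited by the standardized questionnaire at the common visits (SV2 as baseline; weeks 12, 24 and 52). Say explicitly that these are the study visits meant in Section 8.3. Tabulate separately, by arm and source, the AEs found through treatment visits, platform contact or active-arm laboratory panels. Count SAEs from all sources.
- **Consistency.** Sections 6.5.1 and 8.2 give different times for the second daily glucose test (before dinner; four hours after a meal). The passages must be reconciled.

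The cost is SAP wording, since the sensor wear and questionnaires are already scheduled. The main limitation is that the post-baseline windows miss weeks 1 to 11, when diet and medication change most. All-source events in that period must still be reported descriptively by arm. Common windows also leave in place any effect of HIWL + CGM participants acting on their readings; that is part of the intervention rather than a detection artefact.

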8.3 ADVERSE EVENTS AND SERIOUS ADVERSE EVENTS

Participants will be queried for side effects and specific adverse events (AE) at each in-person study visit using a standardized questionnaire. Blinded staff will enter data directly into our centralized study database. Should an AE be detected using this process, or by spontaneous report between visits, or if an AE is detected using physical or laboratory examination, a determination of relatedness to study intervention will be made by the study physician. Serious adverse events (SAE) will be reviewed by the study physician and reported to the IRB per local policy. We will examine the **total number of AEs and SAEs at 12 months** by study group, as well as several subcategories of events.

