3 OBJECTIVES AND ENDPOINTS

OBJECTIVES	ENDPOINTS	JUSTIFICATION FOR ENDPOINTS	PUTATIVE MECHANISMS OF ACTION
Primary			
Test the effectiveness of the combined interventions (data-assisted approach for high intensity medical weight loss) for weight loss in a group of adults with recently diagnosed type 2 diabetes compared to standard of care diabetes self-management education.	Change in body weight (kg) from baseline to 12 months	Body weight is primary target for medical weight loss interventions	
Secondary			
Demonstrate the feasibility of pairing a high intensity medical weight loss treatment for diabetes remission with a digital platform that integrates remote monitoring, patient self-report, and care pathways into a data-assisted and personalized treatment program.	Hemoglobin A1c (%) change from baseline at 3, 6, 9, 12 months; Diabetes remission at 12 months, including partial remission (HbA1c of 5.7-6.4% without the use of anti-diabetes medications) and complete remission (HbA1c of 5.7-6.4% without the use of anti-diabetes medications);	As a result of weight change, we expect to see changes in glycemic control.	Reductions in fat mass due to energy restriction, leading to less insulin requirements and greater use of fat stores to make up the energy deficit.
Tertiary/Exploratory			
Demonstrate the impact of including CGM as part of the remote monitoring system with the data-assisted approach for high intensity medical weight loss treatment.	Patient satisfaction with CGM; length of time to achieve A1c goals; study retention	CGM provides immediate feedback to patients about glycemic control. We expect this to improve behavioral reactions and future choices in a shorter term.	Feedback loops with relevant data and clear actions leading to more decisive improvements in biomarkers.
Compare estimated healthcare expenditures and	EuroQOL-5; healthcare utilization from self-report	Intensive weight loss intervention involves cost and time. However,	Weight reduction could decrease healthcare utilization by resolving

OBJECTIVES	ENDPOINTS	JUSTIFICATION FOR ENDPOINTS	PUTATIVE MECHANISMS OF ACTION
utilization between the active treatment groups and the control intervention	and review of medical records	we might expect cost savings due to reduction in weight and improved glycemic control.	obesity related complications and decreasing need for medications and other healthcare.

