6.5 CONCOMITANT THERAPY

6.5.1 RESCUE THERAPY

Medication adjustment: For participants in the data-assisted HIWL arms, the medical weight loss team will make medication adjustments at the beginning of the intervention, at any subsequent clinic visit or

encounter where the participant reports symptoms of hypoglycemia with corresponding low blood glucose readings, or at quarterly assessments of HbA1c. For participants in the DSME intervention, [name] will meet weekly with the diabetes education interventionist to review participant blood glucose logs and make adjustments in medication dosing. Participants will be asked to self-monitor BG values at least twice daily (fasting and pre-dinner meal), not including additional measures if they are experiencing signs/symptoms of hypoglycemia. At each clinic visit, we will review the average values and ascertain episodes of hypoglycemia, defined as glucose levels less than 70 mg/dL. If the participant reports an episode of severe hypoglycemia (hypoglycemia resulting in a loss of consciousness or inability to self-treat) or symptomatic hypoglycemia on multiple occasions to a non-clinical staff member, one of the study clinicians will be notified to make adjustments in medications within 24 hours per the protocol (Table 4). Medication can be discontinued if the lowest dose available is being prescribed and the average BG \leq 140 or HbA1c $<$ 6.5%. Once total insulin dose is below 20 units daily with adequate control, the participant will be transitioned to an oral medication regimen (i.e., non-insulin).

Table 4. Medication Dose Adjustment Plan			
Event	Action	Follow up	Desired outcome
Initiating weight loss intervention	Reduce meds by up to 50% and/or discontinue all oral hypoglycemic	1 week	No hypoglycemic events and average BG less than or equal to baseline A1c
One episode of severe hypoglycemia or symptomatic hypoglycemia 2 times or more per week	Reduce meds by 50-100%	1 week	No hypoglycemic events
14-day average BG $<$ 126	Reduce meds by 25-50%	2 weeks	Average BG \leq 140
14-day average BG $>$ 140 in absence of hypoglycemia	Increase meds by 25%	2 weeks	Average BG \leq 140 and no hypoglycemia
HbA1c $>$ 7% at quarterly assessment	Increase meds by 25% or add new class	2 weeks	Average BG \leq 154 and no hypoglycemia

7 STUDY INTERVENTION/EXPERIMENTAL MANIPULATION DISCONTINUATION AND PARTICIPANT DISCONTINUATION/WITHDRAWAL

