7.1 DISCONTINUATION OF STUDY INTERVENTION/EXPERIMENTAL MANIPULATION

When a subject discontinues from HIWL, HIWL + CGM, or Control groups, but not from the study, remaining study procedures will be completed as indicated by the study protocol. If a clinically significant finding is identified (including, but not limited to changes from baseline) after enrollment, the investigator or qualified designee will determine if any change in participant management is needed. Any new clinically relevant finding will be reported as an adverse event (AE).

The data to be collected at the time of study intervention discontinuation will include the following:

- The reason(s) for discontinuing the participant from the intervention, and methods for determining the need to discontinue
- If the participant is due to complete assessments within 2 weeks of being discontinued from the study intervention, those assessments will be administered at the time of discontinuation; if the next scheduled assessments are more than 2 weeks from the discontinuation date, the discontinued participant will wait for the next scheduled assessment. Thereafter, the participant will be included in all future scheduled assessments, even though not participating in the intervention.

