7.2 PARTICIPANT DISCONTINUATION/WITHDRAWAL FROM THE STUDY

Participants are free to withdraw from participation in the study at any time upon request.

An investigator may discontinue a participant from the study for the following reasons:

- Initiation of a disqualifying weight loss treatment (e.g., bariatric surgery)
- Lost-to-follow up; unable to contact subject (see **Section 7.3, Lost to Follow-Up**)
- Any event or medical condition or situation occurs such that continued collection of follow-up study data would not be in the best interest of the participant or might require an additional treatment that would confound the interpretation of the study
- The participant meets an exclusion criterion (either newly developed or not previously recognized) that precludes further study participation (e.g., becomes pregnant)

The reason for participant discontinuation or withdrawal from the study will be recorded on the Study Discontinuation Case Report Form (CRF). Subjects who sign the informed consent form and are randomized but do not receive the study intervention may be replaced. Subjects who sign the informed consent form, and are randomized and receive the study intervention, and subsequently withdraw, or are discontinued from the study, will not be replaced.

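### Section 8.3 plans adverse events as event totals by study group; no section plans the number of participants affected

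*Combined protocol and SAP*

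**What the plan says.** Section 8.3 gives the planned AE summary in one sentence: "We will examine the total number of AEs and SAEs at 12 months by study group, as well as several subcategories of events". The subcategories are not named. On collection, the same section says "Participants will be queried for side effects and specific adverse events (AE) at each in-person study visit using a standardized questionnaire"; spontaneous reports and findings on examination or laboratory testing also count. The schedule in Section 1.3 places AE assessment after randomisation at weeks 12, 24 and 52.

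Other sections that touch on harm or on denominators:

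- Section 8.2: "The primary safety assessment will be monitoring of blood glucose and frequency of hypoglycemia". It does not say whether frequency means events, people or a rate.
- Section 8.1, among the measures of glycemic control: "CGM related outcomes that we will assess at baseline and 12 months include time in range, episodes of hypoglycemia, glucose variability, and average glucose".
- Section 9.3 defines the analysis population as those randomised who receive the intervention, without tying it to AEs.
- Section 9.4.1 covers percent weight change, HbA1c and remission. Remission is the only outcome for which it plans a proportion of participants. AEs are not mentioned, and its general promise of confidence intervals for other outcomes sets no AE measure.
- Section 7.1 keeps people who stop the intervention under assessment: "the participant will be included in all future scheduled assessments, even though not participating in the intervention".

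**The concern.** An event total and a count of people affected answer different questions. The first gives the burden of events in an arm, and the second gives the share of the arm that was harmed. A clinician or patient weighing a meal-replacement diet that starts at a minimum of 960 kcal/day (Section 6.1.1), with diabetes medication reduced or stopped at the outset (Section 6.5.1, Table 4), needs the second as well as the first.

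The two can diverge here because events can repeat within a person. Table 4 has an action for "One episode of severe hypoglycemia or symptomatic hypoglycemia 2 times or more per week", so the plan itself allows for participants with several episodes in a week. With 30 per arm, a few such participants could supply most of an arm's total. If only totals are reported, a reader cannot tell this from a harm spread across many people. Leaving the number affected out of the plan also leaves the decision to show it until the data have been seen.

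**Working it through.** The plan gives no AE figure to reproduce: no expected rate, no number affected and no precision. The inputs are the arm size (30 per group, Section 1.1), the three arms (Section 4.1), the 12-month follow-up (Section 4.4) and the loss to follow-up of 10% expected and up to 20% allowed for (Section 9.2). The event counts below are illustrations.

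**1. What a total leaves open.** If E events occur in an arm of n, the number of people affected, k, satisfies 1 ≤ k ≤ min(E, n).

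- E = 12, n = 30: from 1/30 = 3.3% to 12/30 = 40%.
- E = 30, n = 30: from 1/30 = 3.3% to 30/30 = 100%.

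Three ways to reach a total of 12:

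| Pattern | Total | People affected |
|---|---|---|
| 12 people, 1 event each | 12 | 12/30 = 40% |
| 4 people, 3 events each | 12 | 4/30 = 13% |
| 2 people, 6 events each | 12 | 2/30 = 7% |

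Events per person are 12/30 = 0.4 in every row, so dividing the total by the Section 9.3 population does not recover the share affected.

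**2. Could another section supply the number affected?** Section 8.2 gives no unit. The Section 8.1 measure is a glycemic-control outcome taken at two time points, not part of a 12-month AE total. The subcategories in Section 8.3 are subcategories of events. Section 9.4.1 plans a proportion for remission only. None of them fills the gap.

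**3. How much does lost follow-up matter?** Suppose a constant event rate, with a fraction a of one arm leaving after completing on average a fraction f of the year, and no loss in the comparison arm. The total is then lower by (1 − f) × a.

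- f = 0.5: 0.5 × 0.10 = 5%; 0.5 × 0.20 = 10%.
- f = 0.25 (exit at month 3): 0.75 × 0.20 = 15%, which is 0.15 × 12 = 1.8 events out of 12.
- Outer limit, 20% leaving at the very start: 20%, or 2.4 events out of 12.
- 20% against 10% loss at f = 0.5: 1 − 0.90/0.95 = 5.3%.
- Equal loss in both arms: no distortion.

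Unequal loss is an assumption, since Section 9.2 gives overall rates only. The effect is small beside the 3% to 40% range in step 1.

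**4. Precision of the added figure.** Exact (Clopper-Pearson) 95% intervals at n = 30 are 23% to 59% for 12/30 and 1% to 22% for 2/30. The percentages will be imprecise.

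**The case against.** The strongest reply is that Section 8.3 is one descriptive sentence in an assessment section. It does not forbid participant counts, the records exist, no AE test is planned, and the omission can be made good at reporting. That is largely right and keeps the point minor. It does not remove it: the sentence names a specific measure, and followed as written it would not show how many people were harmed.

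Four stronger readings are tempting, and the documents do not support them.

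- *That hypoglycemia is also planned as event totals.* The frequency in Section 8.2 is ambiguous, and the glucose-sensor episodes in Section 8.1 lie outside the AE summary.
- *That continuing complaints will be counted repeatedly.* Table 4 is a dosing rule, and Section 8.3 does not say that a complaint is re-entered at each visit. Section 6.2.1 promises written assessment procedures in a manual that is not among the documents, and a counting rule may be there. The 4-people-by-3-events row above is therefore constructed and forecasts nothing.
- *That totals will be biased by unequal follow-up.* Follow-up is a fixed 12 months in equal arms, assessment continues after the intervention stops, and retention is an exploratory endpoint (Section 3). Step 3 shows a small effect, even under unequal loss that the plan does not predict.
- *That a test on totals would reject too often, or that two HIWL arms would double the count.* No such test is planned, and Section 8.3 reports by study group without pooling.

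**Conclusion.** The point holds, in limited form. The only planned AE summary counts events, and nothing in the plan gives the number of participants affected, so the share of an arm harmed cannot be read from it. For a total of 12 in an arm of 30, that share is fixed only to between 3% and 40%. The bounds follow from arithmetic and need no assumption about rates; the choice of 12 is illustrative. How far totals and people affected will diverge in this trial cannot be known from the documents.

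Severity is minor. No inference is wrong and no data are lost. The conclusion rests on the supplied text; the unseen manual could settle how repeat complaints are counted.

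**What to change.** Extend Section 8.3 to say that, for each of the three randomised arms, the report will show side by side:

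- the number and percent (n/N, with N stated) of participants with at least one AE, at least one SAE, and at least one severe or symptomatic hypoglycemia episode; and
- the total numbers of AEs and SAEs, as already planned.

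Add that a complaint continuing across visits counts once. If loss to follow-up turns out to differ by arm, events per person-year can be added as an optional descriptive line. Poisson or negative binomial models are not needed for a descriptive summary of this size.

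The cost is a few lines of text and one more table, built from records already planned. There are two downsides. The percentages will be imprecise at 30 per arm. Hypoglycemia comparisons involving HIWL + CGM also need a note that this arm is monitored continuously while the others self-test, at a minimum of twice daily (Section 8.2), so a difference may partly reflect detection. The added counts do not correct that.
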